6.1 Study Design

AeroComp is service evaluation exploring the incidence of airway complications amongst patients undergoing general anaesthesia for surgical procedures within NHS Trusts. All adult patients undergoing any surgical procedure (with the exception of obstetric procedures) with the primary method of anaesthesia planned to be general anaesthesia will be eligible for enrolment to this study. The study duration will encompass 5 days (patients being enrolled over a 96 hour consecutive window with a further day of follow-up data collection) with an estimated total of 3600 patients being included. Individual sites are free to choose their own data collection window between 1st November

2021 and 3rd December 2021 as long as the 96 hour window commences at 07:30 on a Monday and closes at 07:29 on a Friday.

Primary outcome:

 Incidence of airway complications at both induction and emergence, defined as a composite of: airway trauma, aspiration, dental/lip/mucosal injury, change of intubation device, desaturation, three or more laryngoscopy attempts, grade 3 or 4 laryngoscopy, difficult face mask ventilation, difficult supraglottic airway device (SAD) usage, emergency front-of-neck airway, failed tracheal intubation, laryngospasm, oesophageal intubation (immediate or delayed recognition), requirement of reintubation immediately after extubation, and need for second intubator.

Secondary outcomes:

- Risk of composite outcome of airway complications will be reported for each individual component of the aerosol precaution bundle.
- Individual complications that comprise the primary outcome.
- Subjective operator assessment of airway difficulty
- Unanticipated airway difficulties necessitating significant deviation from the original airway plan.
- Composite risk of airway complication and association with confirmed/suspected COVID-19 infection, known negative COVID-19 infection without any potential COVID-19 risks, and all other patients.

7 List selection

Operating lists from all participating NHS hospitals will be included, with patients from those lists being eligible. Both elective and emergency cases will be included. The centres and local investigators will be identified by the Pan-London Perioperative Audit and Research Network (PLAN) or other national trainee research networks.

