Additionally, the lead for each site will submit, via the on-line REDCap system, the study week that site has selected (from one of weeks commencing 1st, 8th, 15th, 22nd or 29th November), the total number of eligible procedures for each 24 hour period of the study, and the list of all local investigators involved in the study (to enable production of certificates to demonstrate involvement as well as to allow naming of all collaborators on any manuscripts arising from the study). The site details data capture form is provided in *Appendix 3*.

All investigators and any other individuals contributing to the study will be required to comply with the Data Protection Act 2018 and the NHS code of confidentiality.

Data to be collected:

- Site (automatically populated dependent upon the login credentials of the local investigator)
- Day of the study
- Age of patient (grouped into 18-39, 40-59, 60-79 and \geq 80 years)
- Sex of patient
- American Society of Anesthesiologists (ASA) physical status
- Patient body mass index (BMI), grouped into underweight (< 18.5 kg/m²), normal (18.5 24.9 kg/m²), overweight (25.0 29.9 kg/m²), class 1 obesity (30.0 34.9 kg/m²), class 2 obesity (35.0 39.9 kg/m²), class 3 obesity (>= 40.0 kg/m²)
- Surgical urgency (elective; expedited; urgent; emergency)
- Start time of procedure (first set of observations entered into the anaesthetic record), grouped into daytime (07:30–17:59); evening (18:00–23:59); and overnight (00:00–07:29)
- Surgical specialty
- Surgical severity (minor; intermediate; major)
- Location of procedure: within or outside the main operating theatre complex (including stand-alone day surgery units), used to identify "remote-site anaesthesia".
- Grade of anaesthetist managing airway (initial airway manager and second airway manager if required)
- PPE worn by anaesthetist managing airway:
 - Eye protection: visor; goggles; other

- Respiratory protection: surgical mask; disposable FFP2/3 mask; re-usable FFP2/3 mask; powered air-purifying respirator; other

- Body protection: plastic apron; long-sleeved gown; hazmat suit; other
- Gloves: single pair; double pair; other
- Airway management technique- pre-oxygenation, mask ventilation, apnoeic oxygenation
- Airway equipment utilised to maintain oxygenation and facilitate anaesthesia, divided into:

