 - Desaturation: reduction in oxygen saturations to ≤90% during airway management
 - Severe Desaturation: reduction in oxygen saturations to ≤80% during airway management
 - Difficult mask ventilation: need for two-person (or more) mask ventilation
 - Difficult SAD insertion: multiple insertion attempts; excessive leak; insufficient ventilation; change of SAD size/design

- Failed tracheal intubation even after intervention of a second airway manager, including:

- If oxygenation and provision of anaesthesia was possible via SAD and a decision was made to continue with surgery

- If a decision was made to wake the patient and abandon surgery
- If this resulted in death this should be recorded separately, as above
- Laryngospasm: unwanted muscular response of the larynx that produces partial or complete obstruction of the laryngeal airway [11].
- Oesophageal intubation (recognised): tracheal tube placed in the oesophagus and recognised before delivery of the fourth ventilatory breath
- Oesophageal intubation (delayed recognition): tracheal tube placed in the oesophagus and 4 or more ventilatory breaths delivered.
- Reintubation within 30 minutes of the end of the procedure
- Second airway manager: initial airway manager either requests the assistance of a second individual to directly manage the airway or the supervising anaesthetist requests a second individual to take over management of the airway.
- Emergency front-of-neck airway
- Death due to hypoxia or other complication of airway management.
- Significant deviation from original airway plan
- Subjective assessment of ease of 1) mask ventilation, 2) SAD placement and use, and
 3) tracheal intubation, using a 5-point Likert scale (1-5) with addition of "not attempted" for each question

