10.2 Statistical analysis

Incidence of airway complications amongst the sampled population will be reported as a composite of airway complications as mentioned in **Section 9**.

Continuous data will be reported using means (standard deviation, SD) or medians (interquartile ranges [range]) where appropriate. Categorical data will be reported as numbers (percentages, %) with 95% confidence intervals (CI) calculated using an appropriate method, where applicable. A p value of < 0.05 will be considered as statistically significant. Relationships between categorical variables and outcome measures will be presented as univariate odds ratios with accompanying p-values (Pearson's Chi-square test with Yates' continuity correction). Univariable logistic regression models will be fitted to investigate potential associations between variables describing patient, operator or procedural characteristics and the primary outcome of incidence of airway complications. A multivariable logistic regression model will then be fitted to include all covariates to obtain adjusted association estimates. Variables included in the regression modelling will be selected based on scientific and clinical plausibility of affecting the outcome of airway management.

11 Ethical considerations

This study is designed as a service evaluation, and no ethical approval is expected to be required. As we are collecting routinely captured data with no patient identifiable data, and will not involve either direct patient contact or influence their care in any way, no patient consent will be required. Approval from the Caldicott Guardian at the lead site (Guy's and St. Thomas' NHS Foundation Trust, London, UK), and audit registration at all recruiting centres will be required prior to commencing the project. Participating hospitals will ensure that their local investigators will be appropriately trained, but no GCP certification will be required from investigating teams as this is a service evaluation. The local PI will ensure that no patient identifiable information will be stored during the study.

12 Financing and Insurance

No funding will be required for this study. All investigators will be NHS employees working in their respective trusts and standard NHS Indemnity will apply.

13 Reporting and dissemination

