- 6) Second airway manager: if a second individual took over management of the airway following management by the initial airway manager their grade should be recorded here and "second airway manager required" ticked within the complication section. Leave blank if not applicable.
- 7) Other: this applies to, for example, rigid bronchoscopes, jet ventilators and transnasal humidified rapid-insufflation ventilatory exchange. This should be ticked only if it was the primary airway device following induction of anaesthesia. Typically this will be a planned technique involving pre- +/- per-oxygenation following discussion with the operating surgeon beforehand. Also select if the primary means of oxygenation during the procedure is via a surgically placed jet ventilator (e.g. laryngeal procedures) and no other airway device is placed prior or subsequently by the anaesthetist. The exact device used does not have to be specified.
- 8) Tracheal intubation attempts/laryngoscopy grade should be left blank if intubation is not attempted. The grade here refers to the Cormack and Lehane system as modified by Yentis and Lee, shown below.
- 9) If the patient was not woken up at the end of surgery, emergence complications should not be recorded. If the patient was woken up and then immediately reintubated, this should be recorded as: Woken up: Yes; Reintubation immediately post-procedure: On emergence.
- 10) Only death due to hypoxia or another complication of airway management should be recorded.
- 11) Recognised oesophageal intubation is detected after the first but before the fourth ventilatory breath has been delivered. Delayed recognition is when four or more ventilatory breaths have been delivered.

	1	2		3	
Original Cormack and Lehane system	Full view of the glottis	Partial view of the glottis or arytenoids		Only epiglottis visible	Neither glottis nor epiglottis visible
View at laryngoscopy	E	Y	Y		
Modified system	1 As for original Cormack and Lehane above	2a Partial view of the glottis	2b Arytenoids or posterior part of the vocal cords only just visible	3 As for original Cormack and Lehane above	4 As for original Cormack and Lehane above

E = epiglottis, LI = laryngeal inlet. From Yentis SM, Lee DJH. (1998) Grading of direct laryngoscopy. Anesthesia. 53:1041-4.

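### Operator grade is to be regressed on a composite that counts airway takeovers, one route to which needs a supervised operator, so part of any junior-grade odds ratio may reflect supervision and not airway risk

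*Protocol*

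**What the plan says.** - **Outcome.** Section 6.1 ends its list of composite components with "requirement of reintubation immediately after extubation, and need for second intubator".
- **Definition.** Section 9.1 gives two routes to the second-airway-manager component. The first is a call for help by whoever began managing the airway, and any operator can make it. The second presupposes a supervisor and reads "or the supervising anaesthetist requests a second individual to take over management of the airway".
- **Form.** Appendix 2, note 6, says that "if a second individual took over management of the airway following management by the initial airway manager their grade should be recorded here", and that the component is then to be ticked among the complications. The form has no field for who started the takeover, the reason for it, or whether the operator was supervised.
- **Operator variable.** Section 9.1 collects "Grade of anaesthetist managing airway (initial airway manager and second airway manager if required"). The form bands grade from core trainee to consultant.
- **Analysis.** Section 10.2 fits univariable logistic models to "investigate potential associations between variables describing patient, operator or procedural characteristics and the primary outcome", then a multivariable model with all covariates, at a significance level of 0.05.

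The protocol neither leaves this component out of the operator analysis nor plans a version of that analysis without it.

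**The concern.** An exposure and an outcome should not share a cause that comes from how the outcome is defined. An anaesthetist working alone cannot have a supervisor hand the airway to someone else. An anaesthetist working under supervision can. If junior grades are the ones more often supervised, they have an extra way of reaching the primary outcome that is closed to an unsupervised senior.

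Suppose every other complication were equally common across grades. The grade odds ratio could still exceed 1, because takeovers would add events mainly on the junior side. Adjusting for age, ASA status, BMI or urgency does not help, since the link lies in the outcome. Supervision is not recorded, so it cannot be adjusted for either, and supervisor-initiated takeovers cannot be separated from requests for help after the event.

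At stake is what the evaluation may conclude about grade. A raised odds ratio could be read as higher airway risk with junior operators when some of it describes how they are supervised.

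**Working it through.** **1. The plan's own figures.** Appendix 4 with p = 0.05, d = 0.01, Z = 1.96, N = 1,000,000 and design effect 1:

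n = 1,000,000 × 0.0475 / [(0.0001/3.8416) × 999,999 + 0.0475] = 47,500 / 26.078 = 1821.4, rounded up to 1822, as stated. The expected total also reproduces: 50 centres × 18 procedures × 4 days = 3600. Neither figure is in dispute.

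**2. Inputs for the size of the effect.** From the protocol: 3600 patients and two-sided 0.05. Assumed, because the protocol gives no figure:
- the risk *b* of at least one other component is 5% in both groups. This borrows the protocol's 5%, which is stated for the whole composite;
- takeover occurs at rate *t*, independently of the other components, so *t* is also the rate among cases with no other component;
- 30% to 50% of cases are trainee-led;
- in all rows but the first, the senior rate is one tenth of the trainee rate.

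**3. Formula.** Group risk = b + (1 − b) × t. The odds ratio compares the two group risks.

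Example at 2% v 0.2%: trainee 0.05 + 0.95 × 0.02 = 6.90%; senior 0.05 + 0.95 × 0.002 = 5.19%. Odds ratio = (0.0690/0.9310) / (0.0519/0.9481) = 1.35.

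| Takeover rate, trainee v senior | Composite risk | Odds ratio | Chance of p < 0.05 |
|---|---|---|---|
| 1% v 0% | 5.95% v 5.00% | 1.20 | about 20–22% |
| 2% v 0.2% | 6.90% v 5.19% | 1.35 | 50–55% |
| 3% v 0.3% | 7.85% v 5.29% | 1.53 | 80–86% |
| 5% v 0.5% | 9.75% v 5.48% | 1.87 | over 98% |

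The last column uses a normal approximation with continuity correction, and the range covers the two trainee shares. It ignores clustering by site. In every row the other complications are equally common in both groups.

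**4. Sensitivity to the 5%.**
- With b = 10%, the 2%, 3% and 5% rows give odds ratios of 1.18, 1.27 and 1.45.
- If the protocol's 5% is held as the total for the whole composite, *b* must be lower. At 2% v 0.2% with half the cases trainee-led, the mean takeover rate is 1.1%, so b = (0.05 − 0.011)/(1 − 0.011) = 3.94%. The group risks are then 5.86% v 4.14%, and the odds ratio is 1.44.

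The direction is the same throughout. The size moves with *b* and with the assumed takeover rates.

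**The case against.** The strongest reply is that the overlap is narrow and partly legitimate.

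- **Most of the definition is open to all.** A request for help can come from any grade, consultants included, and note 6 does not mention supervision. A reader might infer that trainee grade is tied to the outcome by definition. The text does not support that: one route of one component needs a supervised operator, and grade is only a proxy for supervision. This stands and limits the claim.
- **The wording implies need.** Section 6.1 speaks of "and need for second intubator" and the form's tick-box says required. A reader might infer that routine teaching handovers will be scored as complications. Note 6 is loose enough to allow it, but nothing in the protocol says that it will happen.
- **Some takeovers are real effects of grade.** Where a junior operator could not secure the airway, the event belongs in the comparison. Early takeover may also avert a third attempt or a desaturation, so a composite without the component can understate junior difficulty. This stands, and it rules out simply replacing one outcome with the other.
- **Takeovers cluster with other difficulty.** If so, few occur alone and the effect shrinks. This is fair, and no rate is available to settle it.
- **Components are reported separately.** Individual complications are secondary outcomes, so a grade signal confined to takeovers might be noticed. That would help interpretation, but it leaves the adjusted grade estimate on the composite as it was.
- **Second-manager grade.** A reader might infer that this field, left blank unless a takeover occurred, would be entered as a covariate and predict the outcome perfectly. No such analysis is planned. Section 10.2 selects variables on plausibility and gives no list, and the final list may sit in a statistical analysis plan that is not shown.
- **Grade is not an objective.** It appears in neither the aims nor the listed secondary outcomes, which lowers the consequence.

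**Conclusion.** The point holds in a limited form. The protocol itself fixes both the outcome definition and the commitment to regress operator characteristics on it, and together they let supervision arrangements contribute to a grade odds ratio. Neither adjustment nor component-level reporting corrects that estimate.

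The possible contribution runs from an odds ratio of about 1.2 to 1.87 over the scenarios with 5% risk of other components. It is smaller if that risk is higher or if isolated takeovers are rarer than 1%. These sizes rest wholly on assumed takeover rates and trainee shares and on independence from the other components. They are illustrations, not estimates. The documents do not show that a grade association would be wholly artefact, nor that the primary incidence or the sample size is wrong. This is an inexpensive improvement to a supporting analysis.

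**What to change.** In Section 10.2, keep the operator models on the full composite and add a pre-specified sensitivity analysis. It repeats the univariable and adjusted operator-grade estimates on the composite without *second airway manager required*. Show the two sets side by side, and state in advance that a grade association will be interpreted as airway risk only if it is present in both. The primary incidence keeps the full composite.

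The cost is a sentence or two of text and one repeat of the grade models on data already collected. The downside is fewer events in the repeat analysis and the possible understatement of junior difficulty described above, so neither estimate should replace the other.

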9.2 Data handling and record keeping

All investigators and study staff will be required to comply with the requirements of the Data Protection Act 2018 with regard to the collection, storage, processing and disclosure of personal information and will uphold the Act's core principles.

Data will be collected onto paper CRFs by either local investigators or the anaesthetic team involved with the case. If local IT capabilities permit, data may be directly uploaded to the data capture service. Local investigators will also upload the total number of eligible patients for each 24 hour period of the study to identify capture rate.

Data will be uploaded by local investigators to the PLAN secure data capture server (https://www.planasm.org/redcap) which is hosted in a secure Tier 2 data centre in London Docklands with regular backup. The interface will use the REDCap v10.4.1 electronic CRF software. A REDCap ID for each patient included will be provided by the system for each new e-CRF uploaded. No uploaded data will contain patient-identifiable information.

All collected data will be anonymised. The following steps have been undertaken to ensure that patients cannot be reidentified from the collected data:

1) All ages are collected in bands.

2) No specific operation/procedure name is collected.

3) The date of surgery is not specifically collected, purely the day of the week upon which it took place in any one of five weeks within the data collection period.

4) No name, hospital number or NHS number is uploaded to the data collection server.

5) All sites are required to register the service evaluation with local Clinical Governance departments prior to recruitment to ensure any local issues are handled appropriately.

6) Caldicott Guardian approval at the lead site has been obtained (available to sites upon request)7) Information Governance approval at the lead site has been obtained (available to sites upon request).

10 Statistical considerations

10.1 Sample size calculation (some pilot/feasibility studies may not require a formal sample size calculation)

Shaw *et al.* [12] reported an incidence of 91 airway complications in 1874 patients (~5%). Therefore, assuming an anticipated 5% incidence of our primary outcome in our study population, a desired error of +/-1% (absolute error) of our estimate for the incidence, and a 95% confidence level of achieving the desired estimate precision, we calculate the sample size required for our study to be \geq 1822 patients (Appendix 4; [13]). For a conservative estimate, with 50 centres each performing 18 procedures a day, we expect 3600 patients to be included, allowing acceptable rates of detection of rare events.

10.2 Statistical analysis

Incidence of airway complications amongst the sampled population will be reported as a composite of airway complications as mentioned in **Section 9**.

Continuous data will be reported using means (standard deviation, SD) or medians (interquartile ranges [range]) where appropriate. Categorical data will be reported as numbers (percentages, %) with 95% confidence intervals (CI) calculated using an appropriate method, where applicable. A p value of < 0.05 will be considered as statistically significant. Relationships between categorical variables and outcome measures will be presented as univariate odds ratios with accompanying p-values (Pearson's Chi-square test with Yates' continuity correction). Univariable logistic regression models will be fitted to investigate potential associations between variables describing patient, operator or procedural characteristics and the primary outcome of incidence of airway complications. A multivariable logistic regression model will then be fitted to include all covariates to obtain adjusted association estimates. Variables included in the regression modelling will be selected based on scientific and clinical plausibility of affecting the outcome of airway management.

11 Ethical considerations

This study is designed as a service evaluation, and no ethical approval is expected to be required. As we are collecting routinely captured data with no patient identifiable data, and will not involve either direct patient contact or influence their care in any way, no patient consent will be required. Approval from the Caldicott Guardian at the lead site (Guy's and St. Thomas' NHS Foundation Trust, London, UK), and audit registration at all recruiting centres will be required prior to commencing the project. Participating hospitals will ensure that their local investigators will be appropriately trained, but no GCP certification will be required from investigating teams as this is a service evaluation. The local PI will ensure that no patient identifiable information will be stored during the study.

12 Financing and Insurance

No funding will be required for this study. All investigators will be NHS employees working in their respective trusts and standard NHS Indemnity will apply.

13 Reporting and dissemination

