15.4 Appendix 4 – Sample Size Calculation

Sample Size for Frequency in a Population

Population size(for finite population correction factor or fpc)(N):	1000000
Hypothesized % frequency of outcome factor in the population (p):	5%+/-1
Confidence limits as % of 100(absolute +/- %)(d):	1%
Design effect (for cluster surveys-DEFF):	1

Sample Size(n) for Various Confidence Levels

Confidence	Level(%)	Sample Size
95%		1822
80%		780
90%		1284
97%		2232
99%		3142
99.9%		5117
99.99%		7142

Equation

Sample size *n* = [DEFF*Np(1-p)]/ [(d²/Z²_{1-q/2}*(N-1)+p*(1-p)]

where

n = sample size

DEFF = design effect from clustered data

N = population size (assumed to be 1 million)

p = the estimated proportion

d = the desired absolute precision

 $1-\alpha$ = the desired confidence level

Z = the Z-score for the corresponding confidence level (normally 1.96 for a 95% confidence level)

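### The named tests and a design effect of 1 treat about 3600 patients from about 50 hospitals as independent, which can inflate error rates for precautions that vary by hospital

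*Protocol*

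**What the plan says.** Section 10.2 relates categorical variables to the outcome by univariate odds ratios, with p-values from "Pearson's Chi-square test with Yates' continuity correction". It continues: "Univariable logistic regression models will be fitted to investigate potential associations between variables describing patient, operator or procedural characteristics" and the primary outcome. A multivariable logistic model follows, and significance is set at p < 0.05. No site term, random effect, GEE or cluster-robust variance is named. The method for the 95% confidence intervals is left open.

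Section 10.1 sizes the study "assuming an anticipated 5% incidence of our primary outcome in our study population", with "a desired error of +/-1% (absolute error) of our estimate for the incidence" and "a 95% confidence level of achieving the desired estimate precision". It expects 3600 patients, "with 50 centres each performing 18 procedures a day". The calculator output in Appendix 4 has a field for the design effect in cluster surveys, and it is set to 1.

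Section 9.1 lists, as the first item collected: "Site (automatically populated dependent upon the login credentials of the local investigator". The second aim in Section 5 is to find components of the aerosol precaution bundle that may go with more complications.

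**The concern.** A chi-square test and an ordinary logistic model take patients as independent. Here they come in groups of about 72 per hospital. If complication rates differ between hospitals, and the use of a precaution does too, the usual standard error for that precaution is too small.

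Such dependence on site is an inference, but the protocol makes it plausible:

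- In Section 9.1, COVID-19 status turns partly on institutional isolation rules and on the patient's pathway, and the Introduction ties the level of PPE to that status.
- Each site collects data in one week of its choice out of five, so calendar time is fixed within a site.
- Eligible patients are found by centre-specific methods (Section 8.1), and local investigators answer for completeness (Section 9.1). Recording of complications may therefore differ between sites.

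The second aim is the most exposed. A PPE item could be flagged because of differences between hospitals, and Section 13 means the findings to inform practice on protecting staff.

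**Working it through.** **Inputs from the protocol.** Incidence p = 0.05, precision d = 0.01 and Z = 1.96 (Section 10.1); "N = population size (assumed to be 1 million", and DEFF = 1 (Appendix 4); 50 centres, 18 cases a day (Section 10.1) and four study days (Section 7).

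**Assumed inputs.** The outcome ICC is not in the documents and is shown at 0.005, 0.01, 0.02 and 0.05. Site sizes are taken as equal.

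**Step 1: the plan's own figures.** n = DEFF·N·p(1−p) / [(d²/Z²)(N−1) + p(1−p)] = 1821.4, rounded up to 1822, as stated. 50 × 18 × 4 = 3600, also as stated, and 3600 / 50 = 72 per centre. The 1822 holds only with DEFF = 1.

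**Step 2: the incidence.** DEFF = 1 + (72 − 1)·ICC. True half-width = 1.96·√(DEFF·0.05·0.95/3600). Coverage of a simple binomial 95% interval = 1 − 2[1 − Φ(1.96/√DEFF)].

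| Outcome ICC | 0.005 | 0.01 | 0.02 | 0.05 |
|---|---|---|---|---|
| DEFF | 1.36 | 1.71 | 2.42 | 4.55 |
| N needed for ±1 point | 2468 | 3115 | 4408 | 8288 |
| Effective N out of 3600 | 2657 | 2105 | 1488 | 791 |
| True half-width (points) | 0.83 | 0.93 | 1.11 | 1.52 |
| Coverage of simple interval | 91% | 87% | 79% | 64% |

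With DEFF = 1 the half-width at 3600 is 0.71 points. The largest design effect that 3600 can absorb is 3600/1821.4 = 1.98, so ±1 point holds up to ICC = (1.98 − 1)/71, about 0.014.

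**Step 3: the association tests.** A beta-binomial simulation was run under no association: 50 sites of 72, 5% outcome, 30% exposure prevalence (assumed), 4000 runs. The entries are rejection rates at nominal 5%.

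| Outcome ICC | 0.005 | 0.01 | 0.02 | 0.05 |
|---|---|---|---|---|
| Exposure set wholly by site, Yates | 7.9% | 12.3% | 18.7% | 34.3% |
| Exposure set wholly by site, Wald logistic | 9.0% | 13.3% | 20.5% | 36.1% |
| Exposure ICC 0.3, Yates | 4.8% | 7.1% | 8.9% | 15.5% |
| Exposure ICC 0.3, Wald logistic | 5.4% | 7.9% | 10.2% | 17.0% |

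For an exposure unrelated to site, the rates stay at 3.8-4.6% (Yates) and 4.7-5.2% (Wald).

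**Check by formula.** For a site-level exposure, 2[1 − Φ(1.96/√DEFF)] gives 9.2% / 13.4% / 20.8% / 35.8%, close to the Wald rows.

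**The case against.** The strongest reply has four parts.

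1. *The interval method is open.* A reader might infer that the interval for the primary incidence will under-cover. The protocol does not say so: Section 10.2 leaves the method to be chosen, and a cluster-adjusted interval would fit its wording. This stands. Only the design effect of 1 points to a simple interval, so the coverage figures are conditional on one being used.

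2. *Handling of site may be in the SAP.* A random intercept is often left to that document. But the protocol does more than stay silent: it names independence-based tests and enters a design effect of 1 in a field meant for clustering. Those are stated choices.

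3. *PPE follows the patient.* The Introduction ties PPE to the patient's COVID-19 status, which varies within hospitals, is recorded, and could enter the multivariable model. This stands in part. A component set wholly by site is the extreme case, and the simulation has no patient-level driver and no covariates. Adjustment for patient factors does not, however, by itself remove the remaining correlation within a site.

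4. *The aims are modest and there is headroom.* The primary aim is descriptive, and 3600 is nearly twice 1822. For the ±1 point target this stands up to an ICC of about 0.014. It does not help the association tests.

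Two other readings are tempting. One is that the hospitals selected themselves; Section 7 says that trainee research networks identify them, and sites choose only their week. How hospitals enter bears on representativeness, not on interval width. The other is that the Yates correction is itself an error. It is a 2×2 device and does not suit variables with several levels, but many technique and equipment items on the CRF are yes/no, and it slightly lowers the inflation above. That point is minor.

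**Conclusion.** As written, the tests, the models and the sample size calculation ignore clustering by hospital although site is available. The consequence is limited to particular places.

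- **Bundle components that vary by hospital.** The 5% level is exceeded if the outcome also clusters. For a component set wholly by site the rate is about 8-9% at an outcome ICC of 0.005 and about 34-36% at 0.05. For a partly clustered component there is no clear inflation at 0.005; from 0.01 to 0.05 the chi-square rate is about 1.4 to 3 times nominal.
- **The incidence.** If a simple binomial interval is used, coverage falls below 95% for any positive ICC.

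A reader might infer that p < 0.05 fails throughout. It does not: covariates unrelated to site keep about 5%. All sizes rest on assumed ICCs and equal site sizes; unequal sizes would lower the ICC at which ±1 point is lost.

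**What to change.** In Section 10.2:

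- Fit the univariable and multivariable logistic models with a random intercept for site, or by GEE with site as the cluster and robust standard errors. Take all odds ratios and p-values from these models in place of the chi-square test.
- Compute the confidence interval for the incidence with a variance clustered on site.
- For PPE and technique components, also report within-site estimates, by site fixed effects or a within/between split. Robust standard errors correct the variance but do not remove confounding by hospital.

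In Appendix 4, replace the single design effect of 1 by a range of assumed ICCs, and restate the precision expected from 3600 patients for each.

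The cost is a change of wording and slightly more analysis work; no new data are needed. Intervals will be wider, and within-site estimates will be imprecise for components that hardly vary within a hospital.
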